5 STUDY ENROLLMENT AND WITHDRAWAL

5.1 *Inclusion and Exclusion Criteria for Persons Living with Dementia*

The investigators will identify and recruit PLWD-CG dyads in which the PLWD has filled a new prescription for an antipsychotic medication. The study programmer will identify potential PLWD-CG dyads using an automated data algorithm that queries claims data and electronic health record (EHR) data on a weekly basis.

Because we will enroll dyads, there are inclusion/exclusion criteria for both persons living with dementia and their caregivers.

Persons with dementia inclusion criteria:

- Aged \geq 65 years
- Diagnosis of Alzheimer's Disease or related dementia (ADRD)
- Expected to live \geq 6 months from enrollment

Persons with dementia exclusion criteria:

- A diagnosis of bipolar disorder or schizopreniform disorder
- The primary care physician's opinion is that the person with dementia is expected to live less than 6 months.
- Primary language is not English (patient requires a translator).

5.2 *Inclusion and Exclusion Criteria for Caregiver Subjects*

Potentially eligible caregivers are identified by the family contact information in the electronic medical record.

Caregiver inclusion criteria:

- Aged \geq 21 years
- Lives with person with dementia or within 8 miles
- Provides at least 8 hours of care per week

Caregiver exclusion criteria:

- Diagnosis of Alzheimer's Disease or related disorders.
- Caregiver is not the spouse or adult child of the person living with dementia
- Primary language is not English (caregiver requires a translator).

5.3 ***Randomization Assignment Procedures***

5.3.1 ***Randomization Procedures***

The study biostatistician will create a randomization schedule and this will be uploaded into a REDCap database. Caregivers who remain eligible for the study after screening will be randomized within REDCap following the pre-set randomization schedule. All eligible caregiver-patient dyads will be block randomized to ensure comparable numbers of dyads enrolled in each study arm. Caregivers will be categorized according to age (<75 years, >=75 years), sex, and spouse/non-spouse.

R, an open-source statistical computing software, will be used to generate an even number of control and intervention assignments within each block.

5.3.2 ***Blinding***

Study staff will be blinded to study arm when verifying subject eligibility.

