7.2.6 Effect of STAR-VTF on CG burden and PLWD antipsychotic medication use.

We will measure overall caregiver burden using the Revised Memory and Problem Behavior Checklist (RMPBC). We will use GEE with a working correlation matrix to estimate the regression model, using robust sandwich estimators to calculate standard errors accounting for within person correlation. We will adjust for baseline pre-randomization covariates: PLWD stage of dementia (DSRS), PLWD FAQ score, PLWD age and sex, caregiver relationship (spouse, non-spouse), caregiver age and sex, and caregiver highest level of education attained.

We will use generalized estimating equations (GEE) with a working correlation matrix to estimate a logistic regression model for refill (versus no refill) of the initial antipsychotic medication. Models will be adjusted for PLWD stage of dementia (DSRS), PLWD FAQ score, PLWD age and sex, caregiver relationship (spouse, non-spouse), caregiver age and sex, and caregiver highest level of education attained, study arm. We will again use GEE with a working correlation matrix to estimate a logistic regression model for daily versus “less than daily” use of antipsychotic medication (as reported to the coach). Models will again be adjusted for pre-randomization variables listed above.

7.2.7 Caregiver depression, stress and self-efficacy.

Caregiver depression will be measured using the PHQ-8. Caregiver self-efficacy will be measured using the Caregiver Mastery Scale. Caregiver stress will be measured using the Kingston Caregiver Stress Scale. We will again use GEE to compare the mean PHQ-8, CMS and Kingston scores in the STAR-VTF and attention control arms. Models will be adjusted for pre-randomization variables as above.

7.3 *Handling of Missing Data*

Preventing missing data is superior to statistical treatment. We will make every effort to collect data on all study participants. If there are substantial missing data or significant loss-to-follow-up, we will use inverse probability weighting(23) to rebalance the STAR-VTF and attention control group. Inverse probability weights are used to rebalance groups on prognostic factors when the treatment and control groups become unbalanced over time, post-randomization, due to study drop out. If we find intermittent missing data, we will instead use multiple imputation(24) via chained equations to address the problem, using at least 10 imputed datasets and combining results using Rubin's rules.

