STAR Caregivers – Virtual Training and Follow-up

Grant Number: 1 R01AG061926-01

Principal Investigator: [name]

STATISTICAL ANALYSIS PLAN

Background/overview/purpose of study:

This is a randomized trial that tests whether receipt of telehealth training for caregivers of people with dementia can reduce utilization of antipsychotic medications, as well as improve the living conditions of both the caregiver as well as the person with dementia.

Scientific questions and outcomes:

1. Is there a change in the rate of antipsychotic medication fills within eight weeks, comparing the intervention to the control arm
 - a. Main measures: Any fill within eight weeks (binary), any refill within eight weeks (binary)
2. Is there a change in standardized scales of caregiver mastery as well as dementia symptoms.
 - a. Primary scales: Revised Memory Problem and Behavior Checklist, Caregiver Mastery, Kingston Caregiver Stress
 - b. Secondary analyses: Dementia Severity Rating Scale subscales

Predictors of interest (independent variable, could be just treatment groups, indicate type as in outcome of interest section):

All analyses will adjust for gender and age, as well as the baseline score. (e.g. the caregiver mastery analysis will adjust for caregiver mastery at baseline) Our variable of interest will be the randomization group.

Unit of analysis:

The dyad of the caregiver and person with dementia.

Other data/analytic specifics (e.g. subgroups of interest, brief discussion of missing data):

Subgroups will be exploratory analyses; we are not specifically powered on any. Missing data will be accounted for via multiple imputation via chained equations, using 100 imputed datasets.

Analytic approach, special Issues and proposed sensitivity analyses:

This is a straightforward randomized trial, so analyses will be run using ordinary least squares regression with empirical standard errors for continuous outcomes, and logistic regression for binomial outcomes. Rubin's Rules will be used to combine results across the multiple imputation datasets.

Analytic software (and version if known):

Stata, version 17.0

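### The SAP's covariate rule omits spouse/non-spouse and does not say whose age and gender it means, so its models match neither the randomization nor Protocol 7.2.6

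*SAP*

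**What the plan says.** **SAP, Predictors of interest.** One rule covers every model: "All analyses will adjust for gender and age, as well as the baseline score". The only illustration is a questionnaire: "the caregiver mastery analysis will adjust for caregiver mastery at baseline". The rule does not say whose gender and age are meant, and caregiver relationship is not mentioned.

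**SAP, Scientific questions and Analytic approach.** Question 1 concerns two yes/no pharmacy measures over eight weeks, a fill and a refill. The method is "logistic regression for binomial outcomes", with least squares and empirical standard errors for the scales. No baseline value is defined for the pharmacy measures.

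**Protocol 5.3.1.** Dyads are block randomized, and "Caregivers will be categorized according to age (<75 years, >=75 years), sex, and spouse/non-spouse". I read these as the strata, although the text does not use that word. Block size is not given.

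**Protocol 7.2.6.** The burden and antipsychotic models both adjust for "caregiver relationship (spouse, non-spouse), caregiver age and sex", along with dementia severity, function, PLWD age and sex, and caregiver education. The antipsychotic analysis is to "estimate a logistic regression model for refill (versus no refill) of the initial antipsychotic medication". No baseline pharmacy variable is listed.

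**Protocol 5.1.** Dyads are recruited because "the PLWD has filled a new prescription for an antipsychotic medication".

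**The concern.** When randomization is balanced within levels of a factor, the treatment estimate no longer varies through chance imbalance in that factor. A model that omits the factor still counts its variation as noise. The standard error is then too large and the test is conservative, to an extent set by how strongly the factor predicts the outcome. The SAP's empirical standard errors do not cure this, because they allow for unequal variances and not for the way arms were assigned.

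The SAP omits one of the three factors outright. If its gender and age are the PLWD's, it omits all three. The protocol's models include all three, so two analysts working from the two documents would fit different models.

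A second gap affects SAP question 1. The rule calls for a baseline score, but a dispensing outcome has no score. If the term is read as whether an antipsychotic had been filled at baseline, the answer is yes for everyone and the term adjusts for nothing.

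**Working it through.** **The plan's own figure.** The only sample size in the documents is for the RMBPC (Protocol 7.1.1): d = 0.65, alpha 0.05 (taken as two-sided), 80% power. The normal formula gives 2 × ((1.960 + 0.842)/0.65)² = 37.2, so 38 per arm. The t-test version gives 38.14, so 39, as stated. Then 39 × 1.3 = 50.7, given as 50. No rate, effect or power is stated for the antipsychotic outcome, so everything below rests on assumptions.

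**Omitted spouse factor, continuous outcome.** Let g be the spouse gap in units of the within-group SD, after the other covariates, and let half the caregivers be spouses. With the factor balanced across arms, the reported standard error is too large by k = √(1 + 0.25g²). Type I error becomes 2 × (1 − Φ(1.96k)). Take 45 per arm (Protocol 7.1 expects up to 90 dyads at 6 months) and d = 0.6. The standard error is √(2/45) = 0.211, so d/SE = 2.846. Power is Φ(2.846 − 1.96) with the factor and Φ(2.846 − 1.96k) without it.

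| g (assumed) | k | Type I error, omitted | Power, included | Power, omitted | Loss, points |
|---|---|---|---|---|---|
| 0.3 | 1.011 | 4.75% | 81.2% | 80.6% | 0.6 |
| 0.5 | 1.031 | 4.3% | 81.2% | 79.6% | 1.7 |
| 0.7 | 1.060 | 3.8% | 81.2% | 77.9% | 3.3 |

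A simulation with stratified blocks of 4 (assumed) agrees. Type I error was 4.7% falling to 3.7% with the factor omitted and about 5% with it included, and 1 to 3 points of power were lost at d = 0.6.

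**Omitted spouse factor, binary outcome.** Logistic regression, 50 per arm, a 50/50 stratum balanced by randomization, 3000 trials per setting. All 50 are kept because Protocol 5.4 still measures antipsychotic use after withdrawal. Each cell gives power without the factor, then with it.

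| Assumed refill, control/STAR-VTF | Spouse OR 1.5 | OR 2 | OR 3 |
|---|---|---|---|
| 60/32% | 83.1, 83.1 | 82.6, 82.7 | 83.9, 84.2 |
| 70/45% | 73.3, 73.4 | 73.5, 73.6 | 73.6, 74.2 |
| 50/25% | 73.7, 74.0 | 74.1, 74.6 | 73.1, 75.2 |

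The gain from inclusion is 0 to 2 points. With 60% in both arms, type I error was 4.5 to 4.9% without the factor and 4.9 to 5.1% with it.

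**Baseline term in question 1.** A design matrix with an intercept, arm and a fill indicator equal to 1 for everyone has rank 2 for 3 columns. On that reading the term drops out.

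**A pharmacy covariate instead.** The candidate is drug supply on hand at randomization. The documents give no supply distribution and no refill rates. In the scenarios below, 50 per arm are split into short and long supply.

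| Assumed refill, control/STAR-VTF | Change in power from adding the supply term |
|---|---|
| Short 80/55%, long 15/15%; 15%, 25% or 40% on long supply | +6 to +8 points (for example 60 to 66%, 51 to 58%, 35 to 42%) |
| Short 80/55%, long 40/25% | +2 to +3 |
| Short 80/55%, long 70/45%, 60/35% or 50/50% | 0 to +2 |
| Short 70/45%, long 30/30% | −1 to +1 |

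The first row implies an AUC for supply of 0.64 to 0.75. A generic continuous predictor shows the same dependence: −1 to 0 points at AUC 0.50, about nothing at 0.60, +2 to +4 at 0.70, +6 to +9 at 0.77 and +9 to +13 at 0.82.

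**The case against.** The strongest reply is that little is lost. A type I error of 3.7% is conservative and not invalid, and it needs a 0.7 SD spouse gap. The SAP already adjusts each scale for its own baseline, which would absorb part of any such gap, so the lower rows of the first table may overstate the cost. For the binary outcome the cost is close to nil. Protocol 7.2.6 also already contains caregiver relationship, age and sex. All of this stands. It limits the size of the point, but the two documents still specify different models.

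A reader might go further and infer that the SAP fixes the baseline term at a constant for question 1 and so gives up power that pharmacy data would restore. The documents do not support that, for three reasons.

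- The SAP speaks of a score and illustrates it with a questionnaire. For dispensing outcomes the term is undefined; it is not set to a constant.
- The 6 to 8 point gain needs the assumed 80% against 15% contrast in control refill rates, an odds ratio of (0.80/0.20)/(0.15/0.85) = 22.7. Milder contrasts give about −1 to +3.
- Supply at randomization matters most for a short window. H2 (Protocol 2.2) is about use at 6 months, by which time most initial supplies would be expected to have run out.

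A simple supply formula, qualifying fill date plus days' supply minus randomization date, also has faults. Protocol 6.2 places a weekly data pull, chart review, prescriber reply, mailed invitation and screening call between fill and randomization, so a refill may come first and the value can be negative. Protocol 7.2.6 anticipates less-than-daily use, for which nominal supply misstates what is on hand.

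**Conclusion.** The point holds as one of alignment. The SAP's rule omits a randomization factor that Protocol 5.3.1 uses and 7.2.6 adjusts for, and it leaves open whether the other two are covered. The cost is modest: about 1 to 3 points of power at d = 0.6 and a type I error between 4.7% and 3.7% for continuous outcomes, and 0 to 2 points for the antipsychotic outcome. These figures assume that the three factors are true strata, blocks of 4, an even spouse split and the stated prognostic strengths. The error is in the conservative direction, so false-positive risk is not raised.

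For question 1, the baseline term is undefined and needs a definition. A material loss of power on that question is not shown. A pharmacy covariate moved power by about −1 to +8 points in the supply scenarios. The larger gains at AUC 0.82 would need a stronger predictor than any of those scenarios implies.

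**What to change.** 1. In the SAP rule, name the three randomization factors in every model: caregiver age group (<75, ≥75), caregiver sex and spouse/non-spouse. State whether PLWD age and sex also stay in, and reconcile the rest of the covariate list with Protocol 7.2.6.
2. For question 1, either define the baseline covariate or say that the baseline-score term does not apply to fill and refill outcomes.
3. Optional: prespecify one pre-randomization pharmacy covariate for the 8-week models, such as supply on hand at randomization counting all fills up to that date, with a rule for negative values. The SAP should also state the day from which the eight weeks run.

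The cost is a sentence or two. The randomization factors are already held; a days' supply field is a reasonable inference from the pharmacy data but is not named in the documents. Item 1 adds one term if the SAP's age and gender are the caregiver's, and three if they are the PLWD's. Item 3 adds one more. With about 100 binary outcomes the model should stay small. Because an adjusted odds ratio depends on its covariates, the list should be fixed before outcome data are seen by arm.
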